6.14. Week 48/Early Termination (ET)

If a subject discontinues study, every attempt should be made to perform the required study-related ET visit and Follow-up visit procedures.

Subject should be instructed **to hold their dose of study drugs** in the morning of the visit. The dose should be taken at the clinic.

Subjects should be instructed to fast (no food or drink, except water [including for study drug intake]), starting from midnight (00:00) or earlier, as appropriate, on the evening prior to Week 48/ET visit to ensure an approximate 8-hour fast prior to the blood sample collection under fasting condition the next morning.

The following assessments will be completed at each visit or as specified in the Schedule of Assessments in [Appendix 2](#).

Note: VAS and Subject reported QOL assessments are recommended to be completed before any other study procedures. Invasive study procedures such as blood draws should be done at the end of a study visit.

- Vital Signs, including weight
- Complete Physical Examination
- ESSDAI
- PE for domains of ESSDAI
- 28 Swollen and Tender Joint count
- Physician's Global Assessment of SjS disease activity
- Physician's Global Assessment of concomitant RA or SLE disease activity as applicable

- Obtain urine sample for:
 - Urinalysis with spot protein/ microalbumin/creatinine
 - Urine Pregnancy Test (female subjects of child bearing potential only)
 - Fasting urine for biomarker
- Obtain blood samples for:
 - Hematology, ESR as applicable, chemistry and hsCRP
 - Viral Monitoring
 - Autoantibodies: deamidated gliadin peptide antibodies (anti DGP IgA or IgG); Anti endomysial antibodies (EMA), RF, CCP, dsDNA, ANA, SSA, SSB, IgA anti tTA (tissue transglutaminase antibodies)
 - Complement (C3, C4, CH50), and CK
 - Cryoglobulins, total Ig, quant IgG, IgA, and IgM, serum and urine immunofixation
 - Fasting lipid profile
 - CCI [REDACTED]
 - CCI [REDACTED]
- VAS
- Subject reported QOLs
- TSQM
- CCI [REDACTED]
- 12-Lead ECG
- PFTs (if available, at selected sites)
- CCI [REDACTED]
- CCI [REDACTED]
- CCI [REDACTED]

- CCI
- Drug accountability
- Adverse Events
- Concomitant medications

6.15. Follow-up Visit

The following procedures will be completed 4 weeks after the subject's last dose of study treatment.

- Vital Signs, including weight
- Symptom-directed PE
- Urine Pregnancy Test (female subjects of child bearing potential only)
- Physician's Global Assessment of SjS disease activity
- Physician's Global Assessment of concomitant RA or SLE disease activity as applicable
- Obtain blood sample for:
 - hematology, ESR as applicable, chemistry and hsCRP
 - Biomarker samples
- VAS
- 12-Lead ECG
- Adverse Events
- Concomitant medications

6.16. Study Assessments

This study consists of 14 scheduled visits plus a follow up visit 4 weeks after study drug is stopped, with total study duration of 48 weeks (+4 weeks).

The study procedures to be conducted for each subject enrolled in the study are described in the following sections. In addition, [Appendix 2](#) presents the study procedures in tabular form.

6.16.1. Patient Reported Outcomes: Visual Analogue Scales and Questionnaires

PROs, including Visual Analogue Scales (VAS) and questionnaires, are to be completed by the subject (where local language questionnaires are available) and should be recommended to be completed before any other study procedures. Please refer to schedule of assessments in [Appendix 2](#) for the time points for which all PRO assessments are to be completed.

6.16.1.1. Global Assessment of Disease Activity

The subject will complete a Global Assessment of Disease Activity, recorded on a 0-100 mm VAS, with 0 indicating “no Sjogren’s Syndrome activity” and 100 indicating “most severe Sjogren’s Syndrome activity”.

For subjects who have concomitant RA or SLE, a second global disease activity VAS will be completed by the subject.

For subjects with concomitant RA: The Global Assessment of Disease Activity will be recorded on a 0-100 mm VAS, with 0 indicating “no Rheumatoid arthritis activity” and 100 indicating “most severe Rheumatoid arthritis activity”.

For subjects with concomitant SLE: The Global Assessment of Disease Activity will be recorded on a 0-100 mm VAS, with 0 indicating “no SLE activity” and 100 indicating “most severe SLE activity”.

6.16.1.2. Assessment of Vaginal Dryness, Ocular Dryness and Oral Dryness

Subjects will complete an assessment of vaginal dryness, ocular dryness and of oral dryness. These assessments will be recorded on 0-100 mm VAS’s, with 0 indicating “no dryness” and 100 indicating “most severe dryness”.

6.16.1.3. Assessment of Pain and Fatigue

Subjects will complete an assessment of overall pain and fatigue related to the underlying disease. These assessments will be recorded on 0-100 mm VAS’s, with 0 indicating “no pain”/“no fatigue” and 100 indicating “most intense pain”/“most severe fatigue”.

6.16.1.4. FACIT-Fatigue Scale

Fatigue will be assessed using the Functional Assessment of Chronic Illness Therapy-Fatigue (FACIT-fatigue) scale. The FACIT-fatigue scale measures an individual’s level of fatigue during their usual daily activities over the past week. It consists of 13 questions with a 7-day recall period on a 5-point Likert scale, with 0 indicating “not at all” and 4 indicating “very much”. The total score ranges from 0 to 52. Higher scores indicate a better the quality of life.

6.16.1.5. 36-Item Short-form Health Survey

The SF-36 is a health related quality of life instrument consisting of 36 questions belonging to 8 domains in 2 components and covers a 4-week recall period:

- physical well-being: 4 domains: physical functioning (10 items), role physical (4 items), bodily pain (2 items), and general health perceptions (5 items)
- mental well-being: 4 domains: vitality (4 items), social functioning (2 items), role emotional (3 items), and mental health (5 items).

The remaining item (health transition) is not part of the above domains, but is kept separately. These scales will be rescaled from 0 to 100 (converting the lowest possible score to 0 and the highest possible score to 100), with higher scores indicating a better quality of life. The SF-36 is not disease specific and has been validated in numerous health states.

6.16.1.6. Exploratory Patient Reported Outcomes

CCI
[REDACTED]

6.16.1.7. EULAR Sjogren's Syndrome Patient Reported Index

EULAR Sjogren's Syndrome Patient Reported Index (ESSPRI) is completed by the patient and it contains just three items to be given an activity level score between 0-10: pain, fatigue and dryness, the final ESSPRI score is the mean of all three scores and therefore also between 0-10.

6.16.1.8. Treatment Satisfaction Questionnaire for Medication

The TSQM is a composite measure based on the subject's rating of medication effectiveness, side effects, and convenience. At Day 1, this questionnaire will be used to assess prior medications used to treat the subject's SjS. At all other time points, specified in the schedule of assessments in [Appendix 2](#), the TSQM will be used to assess the subject's opinion of the study drugs. Site staff should remind the subject of which SjS drugs they should be evaluating at each visit.

6.16.1.9. Oral Health Impact Profile

The Oral Health Impact Profile (OHIP- 14) has been endorsed as a disease specific QOL and measures aspects directly related to oral health and function independent of other problems associated with SjS in 14 questions.

6.16.1.10. Impact of Dry Eye on Everyday Life

Impact of Dry Eye on Everyday Life (IDEEL) is a dry eye questionnaires, that evaluates QOL in subjects with dry eye disease. It covers 57 items organized into 3 modules, Dry Eye Symptom-Bother, Dry Eye Impact on Daily Life, and Dry Eye Treatment Satisfaction, that allow a comprehensive evaluation of the burden of the dry eye condition on patients with SjS.

6.16.1.11. Profile of Fatigue and Discomfort-Sicca Symptoms Inventory

Profile of Fatigue and Discomfort-Sicca Symptoms Inventory (PROFAD-SSI- SF) is questionnaire developed specifically to assess fatigue in SjS patients with 19 questions.

6.16.2. Physician Reported Outcomes: Visual Analogue Scales, Joint Exam and Disease Activity Index

Physician reported outcomes, including VAS, joint exam and disease activity index, are to be completed by the physician, independently of the subject's responses to any PRO assessments. Please refer to schedule of assessments in [Appendix 2](#) for the time points for which all assessments are to be completed.

6.16.2.1. Physician Assessment of Disease Activity

The evaluating physician should complete the global assessment independently of the subject's assessments. The Global Assessment of Disease Activity will be recorded on a 0-100 mm VAS, with 0 indicating "no Sjogren's Syndrome activity" and 100 indicating "most severe Sjogren's Syndrome activity."

For subjects who have concomitant RA or SLE, a second global disease activity VAS will be completed by the provider.

For subjects with concomitant RA: The Global Assessment of Disease Activity will be completed by the provider on a 0-100 mm VAS, with 0 indicating "no Rheumatoid arthritis activity" and 100 indicating "most severe Rheumatoid arthritis activity".

For subjects with concomitant SLE: The Global Assessment of Disease Activity will be completed by the provider on a 0-100 mm VAS, with 0 indicating "no SLE activity" and 100 indicating "most severe SLE activity".

6.16.2.2. Evaluation of Disease Activity: Tender and Swollen Joint Counts

Sites will complete an assessment of tenderness and swelling for 28 of their joints. A list of the 28 joints to be evaluated will be outlined in the site operations manual.

A designated joint assessor with adequate training and experience in performing joint assessments at each study site should perform all joint assessments. The joint assessor should preferably be a rheumatologist; however, if a rheumatologist is not available, he/she should be a health care worker with experience in performing joint assessments. The subject's joint assessor should remain the same throughout the study, as much as possible.

6.16.2.3. EULAR Sjogren's Syndrome Disease Activity Index

EULAR Sjogren's Syndrome Disease Activity Index (ESSDAI) is a disease activity instrument to measure disease activity of primary Sjogren's Syndrome. It consists of 12 domains and each domain is divided into 3–4 levels of activity ([Appendix 8](#)). Definition of each activity level is provided by a detailed description of what should be considered in that item. The ESSDAI should be filled out by the health care provider.

6.16.3. Pulmonary Function Testing

6.16.3.1. Spirometry

Spirometry testing will be performed as outlined in the site operations manual (at selected sites). Please refer to schedule of assessments in [Appendix 2](#) for the time points at which spirometry is to be completed. The following measurements are performed at the visits where spirometry is indicated, where available

- Vital capacity (VC)
- Forced vital capacity (FVC)
- Forced expiratory volume (FEV) at timed intervals of 0.5, 1.0 (FEV₁), 2.0, and 3.0 seconds
- Forced expiratory flow 25–75% (FEF_{25–75})

6.16.4. Clinical Laboratory Evaluations

Hematology, chemistry, urinalysis (with spot protein/microalbumin/creatinine), endocrine, serology, drug screen, hsCRP, TB testing and pregnancy assessments will be carried out as per laboratory assessment table in [Appendix 6](#).

All females of childbearing potential will have urine pregnancy testing every 4 weeks during their study participation. During the periods where study visits are every 6-8 weeks, women of childbearing potential should continue to have pregnancy tests every 4 weeks, using home pregnancy urine tests, which will be provided to them. The site will call the subject every 4 weeks to obtain results of these pregnancy tests and will record the information in the source documents and CRF. If a positive urine pregnancy test is reported, the subject will be asked to stop all study medications and return to the clinic for a serum pregnancy test.

Plasma concentrations of filgotinib (and its metabolite, GS-829845), GS-9876, and GS-4059 will be measured and PK parameters determined.

PK samples will be collected prior to study drug administration (pre-dose) at Weeks 4, 12, and 24; anytime in relation to last study drug administration at Weeks 8, 36, and 48/ET visit. At Week 18, PK samples will be collected approximately 2 hours after study drug administration (post dose).

The samples will be used to evaluate PK of study drug and may also be used to measure protein binding of filgotinib, GS-9876, or GS-4059. Plasma concentrations of other metabolites may be determined, as applicable.

CCI
[Redacted]

Refer to the central laboratory instruction manual for information on collection and shipment of required study samples.

6.16.5. Salivary Flow Measurements

CCI
[Redacted]

6.16.6. Tear Production

CCI
[Redacted]

6.16.7. Parotid Gland Ultrasound

CCI
[Redacted]

6.16.8. Vital Signs

Vital signs will be measured at the time points indicated in the study procedures table ([Appendix 2](#)).

Vital signs should be taken after the subject has been resting for 5 min and are to include HR, respiratory rate, systolic blood pressure, diastolic blood pressure, and body temperature.

6.16.9. Cognitive Test

CCI

Paper questionnaires will be considered source documents.

6.16.10. Physical Examination

A physical examination should be performed at the time points indicated in the study procedures table ([Appendix 2](#)).

Any changes from Baseline will be recorded. Height should be measured at Screening only (subjects should remove shoes). At Screening, Week 24, and Week 48 (or at ET), a complete physical examination should be performed. Symptom-directed physical examinations should be performed at all other visits. Physical exam evaluating the domains of the ESSDAI should be performed at the time points indicated in the schedule of assessments ([Appendix 2](#)).

Weight is measured at all visits.

6.16.11. Other Assessments

12-lead Electrocardiogram

A resting 12-lead ECG should be performed at the time points indicated in the study procedures table ([Appendix 2](#)).

The ECG should be obtained after the subject has been resting in the supine position for 5 min and will include HR, inter-beat (RR), QRS, uncorrected QT, morphology, and rhythm analysis. QT interval corrected for HR according to Fridericia (QTcF) will be derived during the statistical analysis. ECGs will be interpreted by the investigator for clinical significance and results will be entered into the eCRF.

CCI

Ophthalmologic Exams

CCI

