Screening and on-treatment assessments will include: Vital Signs, Physical Examination (PE), 28 Swollen and Tender Joint count, Investigator's Assessment of SjS disease activity, Investigator's global assessment of concomitant Rheumatoid Arthritis (RA) or Systemic Lupus Erythematosus (SLE) disease activity (as applicable), ESSDAI, urine drug screen, pregnancy test (as applicable), CCI [REDACTED], TB testing, chest X-ray (CXR as applicable), CD19+ B cell count (as applicable), HbA1c, Thyroid-Stimulating Hormone (TSH), hematology, Erythrocyte Sedimentation Rate (ESR) as available, chemistry and hsCRP, viral serology and viral monitoring (as applicable), autoantibodies, complement, immunoglobulins, fasting lipid profile, CCI [REDACTED], Patient Reported Outcome (PRO) questionnaires and Visual Analogue Scales (VAS), Pulmonary Function Test (PFT as available), CCI [REDACTED] s test, concomitant medications, Adverse Events (AEs), and at available sites: mCCI [REDACTED]

A resting 12-lead ECG should be performed at Screening, Day 1, Weeks 2, 8, 12, 24, 26, 32, 36 and 48 or ET. ECGs should be interpreted by the investigator (or qualified designee) for clinical significance.

CCI

CCI

CCI

Post treatment follow-up assessments include AEs, concomitant medications, physical examination, 12-lead ECG, vital signs, blood and urine sampling for safety laboratory tests, and urine pregnancy tests (if applicable).

Test Product, Dose, and Mode of Administration:

Filgotinib 200 mg (1 x 200 mg tablet), administered orally once daily
GS-9876 30 mg (1 x 30 mg tablet), administered orally once daily
GS-4059 40 mg (1 x 40 mg tablet), administered orally once daily

Reference Therapy, Dose, and Mode of Administration:

PTM filgotinib (1 x placebo tablet), administered orally once daily
PTM GS-9876 (1 x placebo tablet), administered orally once daily
PTM GS-4059 (1 x placebo tablet), administered orally once daily

Criteria for Evaluation:

Safety:

Safety will be assessed through the reporting of AEs, clinical laboratory tests, PEs, vital sign assessments, and ECGs at various time points during the study.

Efficacy:

The primary endpoint is the proportion of subjects fulfilling protocol-specified response criteria at Week 12, as compared to baseline.

Response is defined as follows:

- For subjects with elevated hsCRP (defined as ≥ 1.5 upper limit of normal (ULN) of hsCRP) at Day 1, subjects are considered to be a responder if they achieve all of the following :

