Safety endpoints will be analyzed by the number and percent of subjects with events or abnormalities for categorical values or 8-number summary (n, mean, SD, median, Q1, Q3, minimum, maximum) for continuous data by treatment group and by study part.

This study will be conducted in accordance with the guidelines of Good Clinical Practice (GCP) including archiving of essential documents.

GLOSSARY OF ABBREVIATIONS AND DEFINITION OF TERMS

ADL	Activities of Daily Living
AE(s)	Adverse Event(s)
AECG	American European Consensus Group
ALT	Alanine Aminotransferase
Anti-SSA	Anti-Sjogren's-syndrome-related antigen A
Anti-SSB	Anti-Sjogren's-syndrome-related antigen B
ATP	adenosine triphosphate
AST	Aspartate Aminotransferase
AUC _{0-τ}	Area under the plasma drug concentration-time curve of a dosing interval
AUROC	Area Under Receiver Operating Characteristic
BCR	B-cell receptor
bDMARD(s)	Biologic Disease Modifying Antirheumatic Drug(s)
BLQ	Below the Limit of Quantitation
BTK	Bruton's tyrosine kinase
C _τ	Trough plasma concentration (just before the next dosing ie pre-dose sample)
C _{ave}	Average observed concentration
CCP	Cyclic citrullinated peptide
csDMARD(s)	Conventional synthetic disease modifying antirheumatic drugs
CFR	Code of Federal Regulations
CIA	Collagen-Induced Arthritis
C _{max}	Maximum observed plasma concentration
CLE	cutaneous lupus erythematosus
CMH	Cochran Mantel Haenszel
CNS	central nervous system
CRO	Contract Research Organization
hsCRP	High sensitivity C-Reactive Protein
CTCAE	Common Terminology Criteria for Adverse Events
CYP	Cytochrome P450
DAS28	Disease Activity Score based on 28 joints
DMARD(s)	Disease-Modifying Antirheumatic Drugs
DNA	Deoxyribonucleic acid
EC ₅₀	Half maximal effective concentration
ECG	electrocardiogram
eCRF	electronic Case Report Form
ESSDAI	EULAR Sjogren's syndrome disease activity index
ESSPRI	EULAR Sjogren's Syndrome Patient Reported Index
ET	Early Termination
EU	European Union

EULAR	European League Against Rheumatism
FACIT-Fatigue	Functional Assessment of Chronic Illness Therapy-Fatigue
FDA	Food and Drug Administration
FEF	Forced expiratory flow
FEV	Forced expiratory volume
FSH	Follicle Stimulating Hormone
FVC	Forced vital capacity
GCP	Good Clinical Practice
GFR	Glomerular filtration rate
GGT	Gamma Glutamyl Transferase
HBsAg	Hepatitis B virus surface antigen
HBV	Hepatitis B virus
HCV	hepatitis C virus
hCG	Human chorionic gonadotropin
HCQ	Hydroxychloroquine
HDL	High Density Lipoprotein

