8.6. Safety Analysis

All safety analyses will be performed using the Safety Analysis Set.

Safety will be evaluated by assessment of clinical laboratory tests, physical examinations, vital signs measurements at various time points during the study, and by the documentation of AEs.

All safety data collected on or after the date that study drug was first dispensed up to the date of last dose of study drug + 30 days will be summarized by treatment group (according to the IMP study drug received).

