7.5. Electrocardiogram Results

A shift table of the investigators' assessment of ECG results at each visit compared with baseline values will be presented by treatment group using the following categories: normal; abnormal, not clinically significant; abnormal, clinically significant; or missing. The number and percentage of subjects in each cross-classification group of the shift table will be presented. Subjects with a missing value at baseline or postbaseline will not be included in the denominator for percentage calculation. No formal statistical testing is planned.

A by-subject listing for ECG assessment results will be provided by subject ID number and visit in chronological order.

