7.7. Changes From Protocol-Specified Safety Analyses

There are no deviations from the protocol-specified safety analyses.

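### The protocol says QTcF will be derived in the analysis, but SAP 7.5 plans no numerical QTcF summary and SAP 7.7 does not record the omission

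*Protocol*

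**What the plan says.** **Protocol.** Section 6.16.11 says the resting ECG "will include HR, inter-beat (RR), QRS, uncorrected QT, morphology, and rhythm analysis". It then says that "QT interval corrected for HR according to Fridericia (QTcF) will be derived during the statistical analysis". The investigator interprets each tracing for clinical significance, and results go into the eCRF. The synopsis gives the schedule: "A resting 12-lead ECG should be performed at Screening, Day 1, Weeks 2, 8, 12, 24, 26, 32, 36 and 48 or ET". Appendix 2 adds the follow-up visit.

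On evaluation, the synopsis says: "Safety will be assessed through the reporting of AEs, clinical laboratory tests, PEs, vital sign assessments, and ECGs". On analysis it says: "Safety endpoints will be analyzed by the number and percent of subjects with events or abnormalities for categorical values or 8-number summary", with the 8-number summary applying to continuous data, by treatment group and study part. Section 8.6, the safety analysis section, is narrower: "Safety will be evaluated by assessment of clinical laboratory tests, physical examinations, vital signs measurements at various time points during the study", together with documented adverse events. It does not name ECGs.

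**SAP.** Section 7.5 plans a shift table in which the investigators' "assessment of ECG results at each visit compared with baseline values will be presented by treatment group". The categories are normal, abnormal without clinical significance, abnormal with clinical significance, and missing. A by-subject listing of ECG assessment results is also planned, and formal testing is excluded. Section 7.7 says: "There are no deviations from the protocol-specified safety analyses".

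**The concern.** The protocol assigns the QTcF derivation to the statistical analysis, and the SAP is where that analysis is specified. The SAP defines RR, QRS, QT, QTc and QTcF as abbreviations, but no visible analysis section uses them. A programmer working from the SAP would produce no QTcF variable.

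A shift table of ratings does not replace it. Each rating is one investigator's judgement of one tracing. If QTcF rose moderately in one arm while most tracings stayed in the same category, the table could show little. It gives no estimate of mean change and no count of subjects beyond a fixed limit. The adverse events of special interest in SAP 7.1.7 include no QT or arrhythmia category that would partly fill the gap.

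At stake is a quantitative safety result for three investigational drugs with a concurrent placebo arm through Week 24. The study report could omit it while stating that no safety analysis had changed.

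**Working it through.** The main check is textual. The arithmetic only sizes what a QTcF summary could show.

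**1. Commitment against plan**

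| Item | Protocol | SAP |
|---|---|---|
| Input data | RR and uncorrected QT are part of the ECG (6.16.11) | Abbreviations only |
| QTcF derivation | To be done in the statistical analysis (6.16.11) | None |
| Summary | ECG is a safety criterion; continuous safety data get an 8-number summary (synopsis) | Shift table of ratings and a listing (7.5) |
| Change recorded | Not applicable | None declared (7.7) |

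QTcF is continuous. Section 6.16.11 promises the derivation, and the two synopsis statements read together imply a summary. SAP 7.5 delivers neither. Sections 7.5 to 7.7 show no redaction that could hide such an analysis. The SAP does record changes elsewhere: Section 6.6 notes the added estimands.

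**2. Data available**

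ECGs fall at Screening, Day 1, Weeks 2, 8, 12, 24, 26, 32, 36 and 48/ET, and follow-up: 2 + 8 + 1 = 11 time points. Four post-baseline ECGs (Weeks 2, 8, 12 and 24) come before placebo subjects switch to active drug, so they have a concurrent placebo comparison.

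**3. Precision at one visit**

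Inputs: 35 subjects per arm (Protocol 3.2 and 8.9). The documents give no SD for change in QTcF; I assume 15 to 20 ms. All 35 per arm are taken to have an ECG at the visit.

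- Standard error of drug minus placebo = SD × √(2/35) = 0.239 × SD. This is 3.6 ms at SD 15 and 4.8 ms at SD 20.
- 95% CI half-width = 1.96 × SE = 0.469 × SD. This is 7.0 ms at SD 15 and 9.4 ms at SD 20.
- Power for a true 10 ms shift (two-sided 5%, normal approximation) ≈ Φ(10/SE − 1.96).
  - SD 15: 10/3.59 = 2.79, and Φ(0.83) is about 80%.
  - SD 20: 10/4.78 = 2.09, and Φ(0.13) is about 55%.

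Missing ECGs would lower both power figures and widen the intervals.

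**The case against.** The best defence of SAP 7.7 is that it speaks of analyses the protocol specifies, and Protocol 8.6 with its subsections specifies none for ECGs. Section 6.16.11 sits under study procedures and says derived, not summarised or compared. This stands in part. A reader might infer that 7.7 is simply untrue; the documents do not support that, because it can be read as covering protocol Section 8 only. Even so, the 6.16.11 sentence refers expressly to the statistical analysis and remains unmet and unexplained.

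A reader might also infer that QT effects go wholly unanalysed. That is too strong. The table separates clinically significant from other abnormalities, a listing is planned, and Protocol 7.5 requires an abnormal ECG with signs or symptoms to be recorded as an adverse event if it meets that definition. What is missing is the quantitative summary.

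Three further points stand:

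- The protocol does not fix ECG time relative to dose. At Weeks 8, 12 and 24 the visit sections (6.6, 6.7, 6.9) hold the dose until the pre-dose PK sample and put blood draws at the end of the visit, so those ECGs probably fall before dosing. That is an inference, and it limits what the data can say about peak exposure.
- Entry of numeric QT and RR in the eCRF is implied but not confirmed.
- The drugs' nonclinical and clinical backgrounds are redacted, so how likely a QT effect is cannot be judged here.

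The SAP cites protocol amendment 1, and the version of the supplied protocol cannot be confirmed. Nothing in the documents suggests that the QTcF sentence was withdrawn.

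**Conclusion.** The point holds as an omission in the SAP: a derivation that the protocol assigns to the analysis is absent, no numerical QTcF summary is planned, and the omission is not recorded. It should be repaired, but it does not touch the primary or secondary efficacy conclusions.

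Its size should not be overstated. It is tempting to say that the trial would readily detect a 10 ms shift. With the assumed SD of 15 to 20 ms and full data on 35 per arm, power is about 80% at the lower SD but only about 55% at the upper, with interval half-widths of about 7 to 9 ms. A descriptive summary would therefore be informative about larger shifts and individual outliers, and only moderately so about a 10 ms mean change. The textual finding does not depend on these figures.

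**What to change.** Add to SAP 7.5, on the Safety Analysis Set:

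- derivation of QTcF from recorded QT and RR by Fridericia's formula, with baseline defined as in SAP 3.8.3;
- 8-number summaries of QTcF value and change from baseline by visit and treatment group for the placebo-controlled period through Week 24, without formal testing;
- counts and percentages of subjects in absolute and change-from-baseline outlier categories, with limits fixed before the Week 24 unblinding.

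The shift table and listing can stay as they are. If the sponsor decides against the addition, SAP 7.7 should state that QTcF is not derived and why.

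The cost is one derived variable and two tables, with no extra visits or procedures, provided numeric QT and RR are in the eCRF; confirm this first. If they are not, the values would have to be retrieved, and recording the omission may be the practical course. The report should note that ECG timing relative to dose was not specified.
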